### Other Pre-specified Outcome Measures

- (13) The proportion of patients discontinuing the opioid, and those with a ≥30% weekly mean increase or decrease in the dose of opioid from baseline during weeks 1-8 and weeks 9-16. Assessment time frame: at baseline, at weeks 8 and 16.
- (14) The proportion of patients with a change from baseline in anti-tumor therapy that could impair the defecation during weeks 1-8 and weeks 9-16. Assessment time frame: at baseline, at weeks 8 and 16.
- (15) Patients' belief in the efficacy of acupuncture. Participants will be asked to answer the following questions at baseline: "Do you think acupuncture will be effective in treating the disease in general?" and "Do you think acupuncture will be effective in improving the OIC?" For each question, patients will choose one of the following answers: "unclear/whatever", "Yes", or "No". Assessment time frame: at baseline.
- (16) Blinding assessment. The blinding is regarded as successful when a patient guesses he/she has received a conventional EA. Before treatment, we told patients that they had a 50% chance of receiving conventional electroacupuncture (EA) with a deeper insertion versus minimal electroacupuncture (SA) a superficial penetration. Conventional electroacupuncture and minimal electroacupuncture have a possible similar efficacy. Both treatments used a relatively small electric intensity, and they may or may not feel the stimulation during treatment. Patients were treated separately to avoid communication. To assess the success of blinding, within 5 minutes after treatment at week 8, patients were asked to guess whether they received conventional EA. Assessment time frame: at week 8.

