### **2.4.1.2 Blinding**

In this study, participants, outcome evaluators, and data analysts will be blinded to the group assignments. The acupuncturists who perform the treatment will not be blinded due to the nature of the acupuncture treatment. Participant blinding will be achieved via a minimal needling at non-acupoints. Bilateral sham points will be attached with the same EA apparatus using a continuous wave of 10Hz and a current intensity of 0.1–0.2mA for 30 minutes after a brief activation period of 30 seconds.

For blinding assessment, all participants will be requested to answer the following question: "Is EA the acupuncture modality that you have received?" within five minutes after any treatment at week 8.

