### 2.4.4 Outcomes Measurement

### 2.4.4.1 Primary Outcome

The primary outcome will be the the proportion of responders, defined as a patient that has  $\geq 3$  SBMs/wk and  $\geq$  increase of 1 SBM from baseline simultaneously for at least 6 out of 8 weeks of the treatment period. SBM refers to a bowel movement that occurred without medication or assistance within the previous 24 hours. When a bowel movement occurs within 24 hours of the use of an optional assisted method (rescue medication or other bowel-treatment regimens) for defecation, it is not regarded as an SBM.

[figure not shown]
Every participant will be required to keep a diary 13 weeks: baseline (run-out period before randomization), 8 weeks of treatment, and 4 weeks of follow-up. Diary entries include the frequency of bowel movements, the consistency of the stool, the difficulty in defecating, the rescue medicine drugs applied and their duration, and the intensity of the cancer pain. During the treatment period, the diary will be collected weekly, and during the follow-up period, it will be collected at the end of week 16. The outcome evaluators will examine the diary content and determine the SBM and frequency accordingly.

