4.4 Statistical Analyses

4.4.1 The General Principle

Summary tables (descriptive statistics and/or frequency tables) will be provided for all variables at different endpoints. For continuous variables, means and standard deviations will be presented, unless the variable has a skewed distribution, in which case medians, 25th and 75th percentiles will be presented. For categorical variables, the number and percentage of participants within each category will be presented. For each variable (continuous or categorical), the number of missing values will be reported.

Statistical Comparisons Between Groups

Continuous variables will be compared using a two-sample *t*-test or Wilcoxon rank-sum test if data show serious deviations from a normal distribution. Categorical data or ordinal data will be compared using a Wilcoxon rank-sum test, chi-square test or Fisher's exact test, as appropriate. All tests will be two-sided.

For the analysis of the primary and secondary outcomes, estimated treatment differences and associated 95% two-sided confidence intervals will be presented.

Analysis Software

For all statistical analyses, SAS 9.4 software will be used. All hypothesis testing will be carried out at the 5% (2-sided) significance level.

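### The blinding success rule in item (16) names no arm, so a correct guess in the EA arm counts as successful blinding

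*Protocol*

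**What the plan says.** Item (16) of the protocol's Other Pre-specified Outcome Measures defines success as follows: "The blinding is regarded as successful when a patient guesses he/she has received a conventional EA". The sentence names no arm. Section 2.4.1.2 (Blinding) says that "all participants will be requested to answer the following question": "Is EA the acupuncture modality that you have received". The answer is taken "within five minutes after any treatment at week 8". The schedule in section 2.4.3 lists the blinding assessment without restricting it to one arm.

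The SAP does not mention the blinding assessment. Its general rules in section 4.4.1 may still reach it: "Summary tables (descriptive statistics and/or frequency tables) will be provided for all variables at different endpoints". They also give numbers and percentages per category and counts of missing values. For group comparisons, "Categorical data or ordinal data will be compared using a Wilcoxon rank-sum test, chi-square test" or Fisher's exact test. Confidence intervals are promised more narrowly: "For the analysis of the primary and secondary outcomes, estimated treatment differences and associated 95% two-sided confidence intervals will be presented". Item (16) is neither a primary nor a secondary outcome.

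**The concern.** Believing that one received conventional EA points towards masking only for a patient who received SA. For a patient who received EA it is the right answer. A rule that scores this answer as success in both arms cannot tell a masked trial from an unmasked one when the EA arm is read alone, or when the arms are combined.

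Participant masking matters here because the primary outcome is built from a diary that the patient keeps, with response required "simultaneously for at least 6 out of 8 weeks of the treatment period". The protocol has real safeguards:

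- the same apparatus is used in both arms;
- patients are treated separately;
- patients are warned that the current might not be felt;
- recent acupuncture users are excluded;
- blinded evaluators determine the bowel movement counts from the diary.

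The arms nevertheless differ in needle depth, which patients are told about, and in whether deqi is sought. Readers will want a usable statement on masking. Under item (16), a report could call blinding successful even though guesses followed the allocation exactly.

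**Working it through.** The documents give no blinding figure, threshold or index, so there is nothing to reproduce. The check applies the stated rule to defined guessing patterns.

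**Inputs**
- Success is a guess of conventional EA, whatever the arm (item (16)).
- Everyone is asked (section 2.4.1.2).
- Allocation is 1:1 (section 2.4.1.1).
- The planned total is 100 with 20% loss to follow-up (section 2.4.1.3). Assumed answers per arm: 100 × 0.8 / 2 = 40. With no loss: 100 / 2 = 50. The figure of 40 assumes that all the loss falls before week 8, although follow-up runs to week 16, so 40 and 50 bracket the planned range.

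**Formulas.** Let gE and gS be the shares guessing EA in the EA and SA arms.
- Success under the rule: gE in the EA arm, gS in the SA arm.
- Pooled success over equal arms (an assumption; no document describes pooling): (gE + gS) / 2.
- Share of guesses that are correct: (gE + 1 − gS) / 2.
- By-arm difference: gE − gS, with a Newcombe 95% CI built from the Wilson limits of each arm.

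**Results**

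| gE / gS | EA-arm success | SA-arm success | Pooled success | Correct guesses | Difference, points (95% CI), 40 per arm | Same, 50 per arm |
|---|---|---|---|---|---|---|
| 100% / 0% | 100% | 0% | 50% | 100% | 100 (88 to 100) | 100 (90 to 100) |
| 80% / 20% | 80% | 20% | 50% | 80% | 60 (39 to 73) | 60 (42 to 72) |
| 50% / 50% | 50% | 50% | 50% | 50% | 0 (-21 to 21) | 0 (-19 to 19) |
| 80% / 80% | 80% | 80% | 80% | 50% | 0 (-18 to 18) | 0 (-16 to 16) |
| 100% / 100% | 100% | 100% | 100% | 50% | 0 (-9 to 9) | 0 (-7 to 7) |

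Example for the first row at 40 per arm, with z² = 3.84. The Wilson lower limit for 40/40 is 40 / 43.84 = 0.912, and the upper limit for 0/40 is 3.84 / 43.84 = 0.088. The lower limit of the difference is 1 − √(0.088² + 0.088²) = 0.876.

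**Reading the table**
1. EA arm alone: the first and last rows both give 100%, although guesses are fully informative in one and carry no information on arm in the other.
2. SA arm alone: 0% against 100% in the same two rows, which is the right direction.
3. Pooled: the first three rows all give 50%, from complete unblinding to coin-toss guessing.
4. Difference between arms: large in the first two rows and zero in the last three. Fisher's exact test at 40 per arm gives p = 1.9 × 10⁻²³ and 1.2 × 10⁻⁷ for the first two rows, and 1.0 for the others.

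**The case against.** The strongest reply is that the useful analysis is largely in place. SAP section 4.4.1, applied to the guesses, yields a by-arm table and a chi-square or Fisher test, and the last line of the working shows that such a test separates the patterns. A misleading claim would need the EA arm to be reported alone or the arms to be pooled, and no document plans either. Item (16) might also be meant as a credibility measure, where similar proportions in the two arms are the reassuring result. Finally, the SAP names no secondary or other outcome individually, so its silence on blinding is not special.

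Most of this stands, and it limits the weight of the point. The answers being collected are sound and can be interpreted once shown by arm. It does not repair the criterion. General rules for tables and tests leave in force a sentence that declares success for a correct guess in the EA arm. The credibility reading is an inference that the documents do not state, and even on that reading the word for success is wrong in that arm. If only the SA arm was meant, the sentence should say so.

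**Conclusion.** The rule is wrong as written. One contrast establishes this without any assumption about sample size or pooling: the EA-arm success rate is 100% whether all patients in the trial know their arm or all believe they received EA. The pooled figures rest on the assumption of pooling over equal arms, and the intervals on 40 or 50 answers per arm.

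The consequence is confined to the statement on participant blinding. The primary estimate and test do not change. This is a modest point, worth correcting because the outcome data originate with the patient and the correction is cheap.

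**What to change.** - **Protocol, item (16):** replace the success sentence with a by-arm assessment: the proportion guessing conventional EA in each arm, and the between-arm difference with a 95% CI. A per-arm blinding index (2gE − 1 for EA, 1 − 2gS for SA) is optional.
- **SAP:** add one line naming this analysis, since the promise of confidence intervals in section 4.4.1 does not extend to item (16).
- **Record of change:** protocol section 12 already lists changes made after the trial began, so log and date this one in the same way.
- **Interpretation:** state that a guess at week 8, the end of the primary outcome window, may partly reflect perceived benefit. A between-arm difference is therefore not by itself proof that masking failed.

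The cost is one short table from yes/no answers already collected, one replaced protocol sentence and one SAP line. No new data are required and the primary analysis stays as it is.

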### 3. Safety Assessment

All adverse events (AEs) will be recorded throughout the whole trial in Adverse Event Form (AEF) by patients themselves and outcome assessors. In our trial, the serious AEs will be defined as events that cause death, exacerbation of the preexisting condition, interruption of treatment, prolongation of existing hospitalization, permanent disability or damage, or required medical intervention to prevent one of the above outcomes. AEs will

be categorized as treatment related or non-treatment related based on its potential association with acupuncture needling procedure by acupuncturists and related specialists within 24 hours. The treatment related AEs defined as follows: dizziness, fainting, localized hematoma, localized minor infection, or some discomforts after acupuncture. Safety assessments also include an 11-point NRS (0 indicates no pain, and 10 indicates the severest pain) to evaluate the intensity of cancer pain. The mean and largest intensity of cancer pain during the preceding week will be evaluated at baseline, as well as weeks 2, 4, 6, 8 and 16.

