### 2.4.2.3 Subject Withdrawals

There will be at least one oncologist or gastroenterologist in each center. They will assess the severe adverse events (SAEs) and then determine whether the participant to continue or terminate the trial. Subjects may leave the study at their own discretion, or the investigator may determine whether it is in the best interest of subjects to withdraw from the trial due to worsening of symptoms, or the occurrence of a serious adverse event.

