- (11) Patients' global assessment of treatment efficacy. Each patient will be asked to rate his/her efficacy of treatment using the following 7-point self-reporting scale: markedly worse (1), moderately worse (2), slightly worse (3), no change (4), slightly improved (5), moderately improved (6), markedly improved (7). Scales with seven response categories are easy to use and have shown a high reliability and validity. This questionnaire will be completed at week 8 and week 16. Assessment time frame: baseline, at weeks 8 and 16.
- (12) The proportion of patients using rescue medicine and the mean frequency of rescue medicine use per week during weeks 1-8 and weeks 9-16. Assessment time frame: at baseline, over weeks 1-8 and 13-16.

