4.3 Rescue medication

During the trial, other medication or intervention for OIC will be discouraged. However,

if a patient has no bowel movement for 72 consecutive hours and cannot tolerate it, only

bisacodyl (5 to 10 mg; up to 20 mg per day) or a 110ml glycerol enema will be permitted

as a rescue medication. Details of drug use (time and frequency) will be recorded.

5. Informed consent

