4.4.5 Safety Analyses

All adverse events and serious adverse events will be listed. Adverse events include the acupuncture-related adverse events and other adverse events.

5. The Summary of Changes of Final SAP

As compared to the original statistical analysis plan (SAP) published in the *Front. Med.* ([name], [name], [name], et al. Effects of Electroacupuncture on Opioid-Induced Constipation in Patients with Cancer: Study Protocol for a Multicenter Randomized Controlled Trial. Front Med. 2022), the present finalized SAP had made a few amendments. The major updates were provided in Table 1.

Table 1. MAJOR UPDATES OF THE ORIGINAL SAP

No.	Item	Original Version	Final Version
1	Missing	Missing data on the primary	As a sensitivity analysis, missing
	data	outcome will be imputed using	data on the primary outcome will be
		the multiple imputation method	imputed using the multiple
		under the missing at random	imputation method under the
		assumption.	missing at random assumption.
2	Primary	The primary outcome will be	The primary outcome will use a
	outcome	evaluated using the x^2 test.	generalized linear model with a
			binomial distribution and identity
			link.
3	Safety	AE incidences for each	AE data will be provided for
	outcome	treatment group will be	descriptive purposes only.
		compared using Fisher's exact	-
		test.

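### The serious-AE definition makes worsening of a preexisting condition and interruption of treatment serious in themselves, so efficacy failure and minor events can enter the SAE listing

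*Protocol*

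**What the plan says.** Protocol Section 3 treats as serious "events that cause death, exacerbation of the preexisting condition, interruption of treatment, prolongation of existing hospitalization, permanent disability or damage, or required medical intervention". The intervention limb ends "required medical intervention to prevent one of the above outcomes". No degree of worsening or length of interruption is specified. The preexisting condition is not defined, so it could mean OIC, the cancer or the cancer pain. The list includes prolongation of an existing admission but names neither a new admission nor a life-threatening event.

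Other sections handle the same events differently:

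- **Protocol 2.4.2.3** gives, as grounds for investigator withdrawal, "due to worsening of symptoms, or the occurrence of a serious adverse event". It also has an oncologist or gastroenterologist assess SAEs and "then determine whether the participant to continue or terminate the trial". That sentence spells out SAE as severe, whereas Section 3 defines serious.
- **Protocol 4.3** permits rescue "if a patient has no bowel movement for 72 consecutive hours and cannot tolerate it, only" specified products.
- **Protocol 2.4.4.2, item (12)** makes rescue a secondary outcome: "The proportion of patients using rescue medicine and the mean frequency of rescue medicine use per week during weeks 1-8 and weeks 9-16".
- **SAP 4.4.5** states: "All adverse events and serious adverse events will be listed". SAP section 5, Table 1, adds that AE data are descriptive only.

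No section says whether worsening OIC or permitted rescue is to be reported as an AE or a serious AE.

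**The concern.** Every participant enters with OIC, and OIC is what the trial tries to improve. A seriousness criterion triggered by any worsening of an existing condition therefore overlaps with the efficacy outcome. A criterion triggered by interruption of treatment has a similar weakness: a small hematoma or a dizzy spell that halts treatment meets it literally, although Section 3 itself lists such events as ordinary treatment-related AEs.

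Three things are at stake. Truly serious events may be diluted by events that are not serious. The seven centers may code the same event differently. And classification may depend on arm, because acupuncturists are unblinded (Protocol 2.4.1.2), assess safety during treatment (2.4.2.4) and take part in judging relatedness (Section 3). Comparing safety is part of the stated purpose (Protocol 2.2), and the listing is the only SAE output that SAP 4.4.5 specifies.

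**Working it through.** **Step 1: the text, case by case.**

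| Event | Section 3 read literally | Elsewhere |
|---|---|---|
| Mild worsening of OIC | Serious: a preexisting condition has worsened | 2.4.2.3 lists worsening separately from a serious AE |
| Minor AE that interrupts treatment | Serious: treatment interrupted | Section 3 lists hematoma, dizziness and the like as treatment-related AEs |
| Rescue laxative or enema | Arguable: serious only if given to prevent a listed outcome | Permitted in 4.3; outcome (12) in 2.4.4.2 |
| Non-responder, bowel habit unchanged | Not serious: nothing has worsened | Primary outcome, 2.4.4.1 |

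The first two rows follow directly from the wording. The third depends on interpretation. The fourth is not caught.

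**Step 2: is rescue a sign of worsening?** Inclusion criterion (7) in Protocol 2.4.2.1 gives an entry frequency of 2 SBMs per week without laxatives. The average gap is 7/2 = 3.5 days = 84 hours, already longer than the 72 hours in 4.3. The time part of the rescue trigger can thus be met by a patient who is no worse than at entry, so rescue use alone does not show an exacerbation.

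**Step 3: the plan's own figures.** The documents give no SAE rate. The only design figure is N = 100 (Protocol 2.4.1.3), from 14% on sham and 14 + 31.4 = 45.4% on EA. Unpooled normal formula, 90% power, two-sided 0.05:

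n = (1.960 + 1.282)² × (0.14×0.86 + 0.454×0.546) / 0.314² = 10.51 × 0.3683 / 0.0986 ≈ 39.3, so 40 per arm; 40/0.80 = 50 per arm; total 100. This reproduces the plan. Expected non-responders are 86% on sham (43 of 50) and 54.6% on EA (27.3 of 50).

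**Step 4: how large could a distortion be?** Illustration only. Assume a background SAE rate *s* in both arms, and a share *f* of non-responders, equal in both arms, who worsen or use rescue *and* are coded serious. Then

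rate = s + (1 − s) × f × (non-response proportion).

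With s = 5%:

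| f | EA | Sham | Gap (sham − EA) |
|---|---|---|---|
| 0 | 5.0% | 5.0% | 0 |
| 10% | 10.2% | 13.2% | 3.0 points |
| 25% | 18.0% | 25.4% | 7.5 points |
| 50% | 30.9% | 45.8% | 14.9 points |

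With s = 10% the gaps run from 0 to 14.1 points. If the arms are equally effective, the gap is 0 at every *f*.

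**Step 5: the opposite direction.** At f = 10% the gap of 3.0 points is 1.5 of 50 patients. Two further EA patients coded serious because a needling event interrupted treatment (2/50 = 4.0 points) would reverse it. At f = 50% the gap is about 7.5 patients, and eight would reverse it. Protocol 4.1 and 4.2 make such an imbalance plausible: EA needles reach the abdominal muscle layer, where sharp pain is expected, with 0.5 to 4 mA for 30 minutes; sham needles go in 2 to 3 mm, with 0.1 to 0.2 mA switched on for only 30 seconds.

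**The case against.** The strongest defence is that the protocol as a whole does not treat efficacy failure as a serious AE. It separates worsening from serious events in 2.4.2.3, tracks rescue as an outcome, and nowhere tells sites to report either as an SAE. It does not say that one missed session is an interruption of treatment. Reporting is descriptive, so no test is affected. AEs are MedDRA-coded (Protocol 7.4), so constipation events could be picked out of the listing. Worsening is already a withdrawal reason in its own right, so a serious-AE label adds little to who leaves the trial.

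Much of this stands, and it limits the consequences. It does not remove the fault: Section 3 is the definition sites are given, and taken at its word it classes mild worsening as serious. The separation in 2.4.2.3 shows a conflict between sections rather than resolving it. Coding would identify constipation events, but not minor events made serious only by an interruption.

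A reader might infer more: that ordinary treatment failure and rescue use become serious AEs, and that sham will therefore look less safe. The documents do not support that. An unchanged non-responder has had no exacerbation. Rescue relieves a state that patients may already have had at entry, and meets the definition only if given to prevent a listed outcome. A sham excess also requires EA to work, such events actually to be coded serious, and no offsetting interruptions on EA.

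**Conclusion.** The point holds as a fault of definition and consistency. Section 3 lets mild worsening of OIC and minor interrupting events be recorded as serious, leaves the coding of rescue open, and conflicts with 2.4.2.3. The SAE listing may therefore mix efficacy failure with harm.

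The size and direction of any between-arm distortion cannot be determined from the documents. The range of 0 to about 15 points rests on an assumed background rate (5 or 10%), an assumed coding share (0 to 50%, equal in both arms) and the planning response rates; it ignores interruptions, which could reverse the sign. The effect is confined to the descriptive safety results and to whatever review 2.4.2.3 attaches to SAEs. The primary efficacy analysis is untouched. The change is worth making because the remedy is cheap.

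**What to change.** 1. In Protocol Section 3, make worsening of a preexisting condition and interruption of treatment serious only when the event also meets a recognised criterion: death, life-threatening, new or prolonged hospitalization, permanent disability or damage, or intervention needed to prevent one of these. Name new hospitalization and life-threatening events explicitly. Deleting the worsening limb alone could lose, for example, a new admission for cancer progression.
2. State that worsening OIC and protocol-permitted rescue are captured as outcomes, and are serious AEs only if they meet one of those criteria.
3. Record AEs leading to interruption or discontinuation in a separate field on the AE form.
4. Reconcile Protocol 2.4.2.3, 2.4.4.2 item (12), Section 3 and 4.3, including whether SAE in 2.4.2.3 means severe or serious.

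The cost is a wording change and one form field, with no extra patients or visits. Events already classified must be re-reviewed against the revised definition, ideally by someone blind to arm.

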### 2.4.2 Subjects

Participants with cancer will be publicly recruited from inpatient and outpatient departments through posters and networks from 6 centers in China.

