#### 4. Interventions

The intervention scheme of this trial is based on our previous trials regarding acupuncture for functional constipation. Acupuncturists who had an acupuncture license and at least 2 years of clinical experience in acupuncture will perform the treatment. We will use disposable acupuncture needles (of the following sizes: 0.30 × 40, 0.30 × 50 and 0.30 × 75 mm) and SDZ-V EA apparatus (all Hwato Brand, Suzhou Medical Appliance Factory, Suzhou, China) in this trial. The duration of the trial for each participant will be 17 weeks: 1- week baseline assessment (run-out period), 8- week treatment and 8- week follow- up.

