### 6. Quality Control

All staff members will undergo training prior to the trial. Monitors will check the case report forms and the acupuncture operation regularly. To improve adherence to intervention protocols, the majority of patients will come from the inpatient setting. The outcomes will be evaluated by independent assessors who are unaware of the group allocation. The data will be input by a clinical research coordinator according to the contents of CRF using the Electronic Data Capture System (EDC), which will be monitored by Clinical Research Associate. Detailed documentation of drop-outs and withdrawals, including the reasons, will be obtained throughout the trial. All of the

investigators will always maintain a strict privacy policy to protect confidentiality before, during and after the trial.

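### The closed definition of a serious adverse event counts a prolonged hospital stay but not a new admission, so some admissions from home can lose the serious label

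*Protocol*

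**What the plan says.** Section 3 of the protocol defines serious adverse events as those that cause death, "exacerbation of the preexisting condition, interruption of treatment, prolongation of existing hospitalization, permanent disability or damage", and ends the list with events that needed medical intervention to prevent one of these. The list has no illustrative wording and no general clause for other important events. Neither the rest of the protocol nor the SAP offers a second definition.

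On care setting, Section 2.4.2 says patients will be "publicly recruited from inpatient and outpatient departments through posters and networks", and Section 2.4.2.4 repeats this. Section 6 adds that "the majority of patients will come from the inpatient setting". No outpatient number or share is given.

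On duration, Section 4 sets a one-week baseline, then "8- week treatment and 8- week follow- up". The assessment schedule in Section 2.4.3 collects adverse events through weeks 9-16.

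On use of the category, SAP 4.4.5 lists adverse events and serious adverse events. Section 2.4.2.3 of the protocol says of the site oncologist or gastroenterologist: "They will assess the severe adverse events (SAEs) and then determine whether the participant to continue or terminate the trial".

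**The concern.** For a patient living at home when an event starts, the hospital criterion cannot be met, because there is no existing stay to prolong. The label then rests on the remaining criteria. Two patients with the same event can be classed differently only because one was already in hospital.

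Two things are at stake. The SAP treats adverse event data as descriptive (final-version column of the table in SAP Section 5), so the serious event listing is a main safety output and should mean the same for every patient. And if the specialist review in Section 2.4.2.3 is driven by the serious category, an event without the label may not reach it.

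**Working it through.** No arithmetic in the plan bears on this beyond the timeline: 1 + 8 + 8 = 17 weeks in all, of which 8 + 8 = 16 follow randomization and the last 8 (weeks 9-16) have no trial sessions. The check is to take each criterion in Section 3 and ask whether it applies to one test event in two patients. The test event is an acute illness in weeks 9-16, unrelated to the cancer or the constipation, that resolves without lasting damage and needed no intervention to avert a listed outcome.

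| Criterion in Section 3 | Inpatient whose stay is extended | Patient admitted from home |
|---|---|---|
| Death | no | no |
| Exacerbation of an existing condition | no (unrelated event) | no (unrelated event) |
| Interruption of treatment | no, if this means trial sessions | no, if this means trial sessions |
| Prolonged existing stay | **yes** | **cannot apply** |
| Permanent disability or damage | no | no |
| Intervention to prevent a listed outcome | no | no; admission is not itself a listed outcome |
| **Result** | **serious** | **not serious** |

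The two columns differ in one row only, and that row turns on where the patient was when the event began.

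Three points set the boundaries of the result:

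1. In weeks 1-8 there are three sessions a week (Section 4.2), 24 in all. An admission would often interrupt them and so qualify by that route. The gap lies mainly in weeks 9-16.
2. The protocol does not say which treatment the interruption clause means. If it covers therapy other than trial sessions, more admissions in weeks 9-16 qualify and the gap narrows.
3. The gap is not confined to those recruited as outpatients. An inpatient who goes home and is later readmitted is in the same position.

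**The case against.** The strongest reply is that the other criteria are broad. Every participant has cancer and constipation, and the exacerbation clause has no severity threshold. The interruption clause covers much of weeks 1-8. The intervention clause covers events that could have led to death or permanent damage if untreated. Bowel obstruction, the example a reader might reach for first, could qualify under any of the three. This stands, and it limits the point to admissions that meet no other criterion.

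It is also true that all adverse events are recorded throughout the trial whether serious or not, that relatedness is judged within 24 hours for all of them, and that Section 2.4.2.3 separately allows withdrawal for worsening symptoms. This stands too: the event stays in the data and patient protection does not rest on the label alone. Section 2.4.2.3 moreover speaks of severe events where Section 3 defines serious ones, so it is not certain that the Section 3 list triggers the specialist review.

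A reader might infer three stronger things that the documents do not support:

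- **That serious event counts will reflect care setting rather than severity.** Setting decides the label only for the residual events.
- **A number of missed events.** Assuming 20 to 40 outpatients among 100 patients and 10% to 30% of them admitted gives 20 × 0.10 = 2 to 40 × 0.30 = 12 admissions. Both inputs are assumptions. The product counts all such admissions, not those that fail every other criterion. Under the same inputs the number missed could be near zero, and readmitted inpatients are not in the sum.
- **A bias between arms.** Nothing in the plan suggests that the gap favours one arm, and no between-group test of adverse events is planned.

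None of this removes the inconsistency. It reduces its reach.

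**Conclusion.** The concern holds in a limited form. The definition is closed, its only hospital criterion is prolongation, and the trial enrols people who are not in hospital. A new admission that meets no other listed criterion is non-serious on the text, while the same event extending an inpatient stay is serious. Such events remain recorded as adverse events, but can be absent from the serious event listing and may not reach specialist review.

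Their number cannot be estimated: the documents give neither the outpatient share (only that it is a minority) nor any admission rate. The conclusion rests on reading the list as exhaustive and, for weeks 9-16, on reading the interruption clause as referring to trial sessions. The point does not touch the primary outcome. It is worth correcting because it concerns a safety definition and the correction is small.

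**What to change.** Amend the definition in protocol Section 3, and the adverse event form, so that a new hospital admission counts in the same way as prolongation of an existing one. State that this same definition governs the specialist assessment in Section 2.4.2.3, resolving the severe/serious wording there, and the listing in SAP 4.4.5.

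Before database lock, go through the recorded adverse events and reclassify those with a new admission. The blinded data review meeting in Section 7.6 is a natural place to confirm the result. Reclassification works only where the form or source records show that an admission took place, so that should be checked as well.

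The cost is one phrase in Section 3, a matching item on the form, one pass through the recorded events, and slightly more serious adverse event processing. No outcome, sample size or efficacy analysis changes.
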